Deep brain stimulation (DBS) has become an evidence-based treatment for movement disorders such as Parkinson's disease. Recent animal studies of DBS suggest that neuronal subpopulations may be specifically activated by burst-type DBS and that this type of electrical stimulation programming may improve the efficacy and durability of DBS. Burst-type DBS is defined as a novel stimulation protocol in which intermittent bursts of traditional high-frequency rectangular wave stimulation are delivered. Implanted pulse generators (IPGs) have the capability to deliver such stimulation by setting specific "on" and "off" times, however there is no published human data on the results of such programming in patients undergoing DBS for movement disorders such as PD.

Primary Objective

The primary objective is to determine change in the UPDRS-III motor score in the medication OFF state with burst-type DBS programming in the acute setting (after 30 minutes) and then after 6 months and 12 months for patients with bilateral subthalamic nucleus DBS for Parkinson's disease.

Study Design:

Randomized, double-blind cross-over study with N= 5 patients implanted with bilateral subthalamic nucleus DBS.

Study Site:

Allegheny General Hospital
Neuroscience Institute
[name]
[name]

Study Population

Patients for this study (N= 5) should have bilateral STN-DBS (with Boston scientific Gevia or Genus technology) implanted for Parkinson's disease. The patients should be on stable DBS programming settings and stable medication regimens defined as no DBS programming changes or Parkinson's disease medication changes over past 2 weeks. The DBS implantation should have been performed by either [name], MD or [name], MD at Allegheny General Hospital and implantation surgery must have occurred a minimum of 6 months prior to the day of enrollment.

Recruitment Strategy

Subjects will be recruited from the DBS practice of investigator neurosurgeons [name] MD and [name] MD. Patients will be identified by the neurosurgeons as well as by DBS nurse [name] RN and physician assistant [name] PA-C.

Recruitment will stop when approximately 5 subjects are enrolled. It is expected that approximately 15 subjects will be enrolled to produce 5 evaluable subjects.

Subject Replacement

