In the event that consented subjects are unable to complete study procedures for any reason (e.g. unable to attend visits, adverse reaction to burst programming, or other concerns determined by primary investigator), subjects will be withdrawn from the study and primary investigator may screen and enroll replacement subjects(s) to ensure the number of completed subjects equals 5.

Inclusion Criteria

1. Adult patients (male and female) ages 18-85
2. Bilateral DBS-STN (subthalamic nucleus) target for idiopathic Parkinson's disease implanted minimum 6 months prior to the day of study enrollment
3. Stable DBS programming settings and Parkinson's disease medications defined as no changes to either within past 2 weeks
4. Comfortable using DBS controller to turn off device prior to study visits
5. Able to provide informed consent and complete follow-up visits

Exclusion Criteria

1. DBS technology other than Boston scientific Genus/Gevia
2. Unable to complete follow-up visits
3. DBS brain targets other than STN (subthalamic nucleus)
4. Signs of progressive cognitive decline

Subject Completion/Withdrawal

Subjects may withdraw from the study at any time without prejudice to their care. They may also be discontinued from the study at the discretion of the Investigator for lack of adherence to study treatment or visit schedules, AEs, or due to medical illness which complicates follow-up. The Investigator or the Sponsor (if applicable) may also withdraw subjects who violate the study plan, or to protect the subject for reasons of safety or for administrative reasons. It will be documented whether or not each subject completes the clinical study. If the Investigator becomes aware of any serious, related adverse events after the subject completes or withdraws from the study, they will be recorded in the source documents and on the CRF.

The study duration per subject will be up to 365 days.

Description of Devices and Assessments

DBS System

Boston Scientific Neuromodulation (BSN) Vercise™ System: A neurostimulation device consisting of an implantable pulse generator (IPG), integrated rechargeable battery, two DBS leads, two DBS extensions, Burr Hole Cover, surgical tools, GUIDE XT Software and external devices (programming system, remote control, and charging system). The implanted pulse generator (IPG) for this study will be either the Gevia or Genus model.

UPDRS (United Parkinson's Disease Rating Scale)

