- Unblinded examiner will then turn the DBS ON to the patient's baseline DBS settings continuously ON or to burst DBS mode (baseline DBS settings for the patient with DBS set to 1 sec ON, 4 sec OFF), based on results of randomization. The patient will be blinded to this programming change and will be kept at this initial setting for 30 minutes.
- Next, a blinded examiner who did not perform the programming change will perform a UPDRS-III evaluation. Next, the DBS will be turned off for 15 minutes to permit for a washout period.
- Next, the DBS will be turned on by the unblinded examiner to the alternate setting (burst DBS in case that the patient first was turned on with their baseline DBS setting or baseline DBS setting in case that the patient was first turned on with burst DBS setting) and kept on this setting for 30 minutes.
- After 30 minutes, the blinded examiner will perform another UPDRS-III evaluation. Patients, who are blinded to the stimulation setting, will be asked if they preferred one stimulation mode over the other.
- If any adverse events occur with burst DBS mode, the unblinded examiner will decrease the amplitude of the DBS by 0.5mA increments until the adverse events abate. If there are not persistent adverse events with 30 minutes of burst DBS mode, the patient will be kept in burst DBS mode at the end of first visit and will be allowed to take their Parkinson's disease medications.

Figure 1. Visit 1 Assessment Schema

Randomization Procedure

Subjects will be randomized to determine which DBS setting is initially programmed during visit one. All subjects will be programmed to both settings over the course of the visit, but the order is randomized to ensure appropriate blinding of the UPDRS assessor. Subjects have a 50% chance of being randomized to the “burst” mode, and a 50% chance of being randomized to the “baseline” mode. Following the initial UPDRS assessment (Meds OFF/DBS OFF), the study coordinator or unblinded assessor will use a computerized randomization system to determine which DBS setting the subject receives first.

Visit Two (6 months +/- 30 Days)

- Parkinson’s disease dopaminergic medications will be withdrawn overnight to establish medication-OFF state and DBS will be turned OFF overnight for establishing DBS-OFF state.

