- Examiner will establish a UPDRS-III baseline with medication-OFF, DBS-OFF state. Examiner will then turn the DBS ON to the burst DBS state and keep ON for 30 minutes. After 30 minutes the examiner will perform another UPDRS-III evaluation and will ask about any adverse effects. Patients will then be allowed to take their Parkinson’s disease medications and will be kept on the burst mode DBS state.
- Patients will be asked if they prefer the burst mode DBS state to their baseline settings before the study.

Visit Three (12 months +/- 30 days)

- Parkinson’s disease dopaminergic medications will be withdrawn overnight to establish medication-OFF state and DBS will be turned OFF overnight for establishing DBS-OFF state.
- Examiner will establish a UPDRS-III baseline with medication-OFF, DBS-OFF state. Examiner will then turn the DBS ON to the burst DBS state and keep ON for 30 minutes. After 30 minutes the examiner will perform another UPDRS-III evaluation and will ask about any adverse effects. Patients will then be allowed to take their Parkinson’s disease medications and will be kept on the burst mode DBS state.
- Patients will be asked if they prefer the burst mode DBS state to their baseline settings before the study. At the conclusion of the study, patients will be asked if they want to continue to use burst DBS state or if would prefer to be programmed back to their pre-study baseline DBS settings.

Phone Follow-Up Visits

Phone follow up calls will be completed by study personnel to determine subject’s programming preference at 1 week, 1, 3 and 9 months post programming changes.

Table 1. Schedule of Study Events

Activities	Screening/ Enrollment	Visit 1 (Baseline)	Visit 2 Month 6 +/- 30 days	Visit 3 Month 12 +/- 30 days	Phone Follow-up ⁴
Informed Consent	x				
Demographics	x				
Medical History	x				
Parkinson's Medications	x	x	x	x	x
Concomitant medications	x	x	x	x	x
Adverse Events		x	x	x	x
Serious Adverse Events		x	x	x	x
Adverse Device Effects		x	x	x	
UPDRS III (Meds OFF ¹ /DBS OFF ²)		x	x	x	
UPDRS III (Meds OFF ¹ /DBS ON- Burst)		x	x	x	
UPDRS III (Meds OFF ¹ /DBS ON- Baseline ³)		x			

¹ Parkinson's disease dopaminergic medications should be withdrawn overnight to establish medication-OFF state

² DBS should be turned off overnight to establish DBS-OFF state

³ DBS should be programmed to the baseline settings patient had before study entry

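### The randomised, double-blind crossover label fits only the 30-minute comparison at Visit 1, not the 6- and 12-month parts of the primary objective

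*Combined protocol and SAP*

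**What the plan says.** The Study Design section describes a "Randomized, double-blind cross-over study with N= 5 patients implanted with bilateral subthalamic nucleus DBS" and exempts no part of the study from that description. The Primary Objective is the change in medication-OFF UPDRS-III with burst programming "in the acute setting (after 30 minutes) and then after 6 months and 12 months for patients with bilateral subthalamic nucleus DBS". It does not say what burst is compared with.

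The Randomization Procedure is confined to the first visit: "Subjects will be randomized to determine which DBS setting is initially programmed during visit one". In the Visit One section, an unblinded examiner programs the device, the patient is blinded to the setting, and "a blinded examiner who did not perform the programming change will perform a UPDRS-III evaluation". Both settings are rated, each after 30 minutes.

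For Visits Two and Three the text names one role, an examiner, who takes a DBS-OFF rating. Then: "Examiner will then turn the DBS ON to the burst DBS state and keep ON for 30 minutes". The examiner rates again, and the patient is left on burst. Table 1 marks the rating under the pre-study settings at Visit 1 only.

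Statistical Methods names the Mann-Whitney U test and a 0.05 threshold, but no contrast or time point. Risk Assessment lets any patient stop burst after the first visit. Under Subject Replacement, withdrawal reasons include an adverse reaction to burst, and the "primary investigator may screen and enroll replacement subjects(s) to ensure the number of completed subjects equals 5".

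**The concern.** A reader who sees the label and the three-part primary objective will expect each time point to carry a randomised, blinded comparison with the patient's usual stimulation. Two of the three do not. As the plan stands, a 12-month change from OFF to burst could be reported at p < 0.05 as a primary result of a randomised, double-blind crossover. It could then be taken as evidence that burst matches or beats usual stimulation, a question those visits are not set up to answer.

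Two features add to this. UPDRS-III is scored by an examiner, so unstated blinding at the later visits matters for the endpoint itself. And patients who fare badly on burst have routes out of it, or out of the study, before month 6.

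**Working it through.** The documents give no effect size, standard deviation or power for N = 5, so there is no planned figure to reproduce and no way to express the problem in UPDRS points. The check is a count of planned ratings and a reading of the sections side by side.

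**Planned UPDRS-III ratings per patient** (Table 1, with the visit descriptions):

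| | Visit 1 | Visit 2 | Visit 3 | Total |
|---|---|---|---|---|
| DBS OFF | 1 | 1 | 1 | 3 |
| DBS ON, burst | 1 | 1 | 1 | 3 |
| DBS ON, usual setting | 1 | 0 | 0 | 1 |
| All | 3 | 2 | 2 | 7 |
| In random order with a stated blinded rater | 2 | 0 | 0 | 2 |

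- Stimulation-ON ratings: 2 + 1 + 1 = 4. In random order with a stated blinded rater: 2 of 4, both at Visit 1; 0 of the 2 at Visits 2 and 3.
- Primary time points with a randomised, blinded burst-versus-usual comparison: 1 of 3.

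**Does another section extend the blinding?** DBS Programming Procedure says patients will not know which electrodes are active. That concerns patients and electrodes, not stimulation mode and not the rater. In Appendix A, the Visit 1 form has an unblinded-examiner section and a field for the randomised setting; the form for Visits 2 and 3 has neither. At both later visits patients are asked whether they prefer burst to their pre-study settings, which suggests that they know the mode.

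**Contrasts available at months 6 and 12**

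- Burst minus OFF at the same visit: available, in fixed order (OFF, then burst), without stated blinding.
- Later burst minus the Visit 1 usual-setting score: can be computed, but mixes mode with 6 to 12 months of elapsed time, possible disease or medication change, and a difference in what the rater may know.
- Burst minus usual setting at the same visit: not available.

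**The named test.** Each patient supplies both scores at Visit 1. A Mann-Whitney U test of burst scores against usual-setting scores treats them as coming from independent groups. The smallest attainable exact two-sided p-values with 5 patients are:

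- Mann-Whitney, 5 against 5, ignoring the pairing: 2 / C(10,5) = 2/252 = 0.0079.
- Signed-rank on 5 paired differences: 2 / 2^5 = 0.0625.
- Signed-rank on 6 pairs, if one withdrawn patient also had both Visit 1 ratings: 2 / 2^6 = 0.031.

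A rank-sum test can respect the crossover if it compares period differences between the two order groups. With the best split of 3 and 2, its smallest two-sided p is 2 / C(5,2) = 0.2. The plan does not say this is meant.

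**The case against.** The strongest reply is that the objective concerns change with burst and names no comparator. If the intended change at months 6 and 12 is burst against OFF, those visits need no usual-setting rating. That stands as far as it goes. But the protocol does not say so, and a fixed OFF-then-burst sequence without stated blinding still does not match the label.

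Second, blinding at the later visits is unstated rather than denied. The bare word examiner is also used for the Visit 1 OFF rating, so it need not mean that one person both programs and rates. This too is fair: the documents do not establish that the later rater is unblinded. They give no support for calling the rating blinded, and burst is the only mode used.

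Third, the Randomization Procedure states its Visit 1 scope openly. So it does. The conflict lies with the study-wide label and the three-part primary objective.

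Some stronger readings are tempting but not supported:

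- *Months 6 and 12 can say nothing about the usual setting.* The comparison with the Visit 1 score exists; it is confounded, not impossible.
- *Only patients who stayed on burst contribute later, and every later OFF score follows months of burst.* Risk Assessment treats stopping burst and leaving the study as separate events, and the protocol does not say whether patients who stop burst are still rated.
- *About 10 randomised pairs will be lost.* A reader might infer this from "It is expected that approximately 15 subjects will be enrolled to produce 5 evaluable subjects". The preceding sentence has recruitment stop at about 5 enrolled, the 15 may include patients who never reach Visit 1, and no completers-only analysis is specified.
- *Carry-over from burst shrinks the later change.* The rationale that "this type of electrical stimulation programming may improve the efficacy and durability of DBS" makes this possible. However, DBS is off overnight before each visit, and disease progression could move the OFF score the other way.

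**Conclusion.** The point holds and should be fixed. The labelled design is present at 1 of 3 primary time points and for 2 of 4 stimulation-ON ratings. Months 6 and 12 are, as written, uncontrolled follow-up with no stated blinding. They support a same-visit burst-minus-OFF description, not a claim about burst against the usual setting. The later visits may under-represent patients who did poorly on burst; by how much cannot be determined from the documents.

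The Visit 1 comparison is randomised and blinded as described. Its weakness is in the analysis: no contrast is named, and the stated test, applied to the two sets of scores, ignores the pairing.

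The conclusion rests on the text being complete about Visits 2 and 3. A written statement of a blinded rater there would change the description of the blinding. It would not supply random order or a same-visit usual-setting rating.

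**What to change.** 1. Apply the randomised, double-blind crossover description to Visit 1 only. Name the within-patient Visit 1 burst-minus-usual difference as the randomised contrast. Analyse it as paired data in every patient with both Visit 1 stimulation-ON ratings, including those later withdrawn or replaced. Report each patient's difference with the order received, and an estimate with a confidence interval.
2. Describe months 6 and 12 as uncontrolled follow-up, and as open-label unless the protocol states a blinded rater. Separating programmer from rater would not by itself blind the rating, because burst is the only mode given. Report OFF, burst and burst-minus-OFF scores descriptively, with no p < 0.05 claim of burst against the usual setting.
3. State whether patients who stop burst are still rated. Report the mode each patient was using before each visit, and the numbers and reasons for stopping burst, withdrawal and replacement. Mention carry-over into the OFF score only as a possibility, alongside the overnight DBS-OFF period and disease progression.

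**Cost.** No added visit, test, patient or staff member is needed; Visit 1 scores of withdrawn patients must be kept. The change is more than editorial, because the 6- and 12-month results become descriptive, and the sponsor has to accept that. With exactly 5 pairs, an exact two-sided signed-rank test cannot reach 0.05, so the Visit 1 result should rest on the estimate and its interval.

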Adverse event information will be collected throughout the study, beginning once the patient is enrolled in the study and monitored until each event is adequately resolved or explained. An AE or SAE description (including the nature of the event, date and time of onset, determination of non-serious versus serious, intensity, duration, causality, and outcome of the event) will be recorded on the case report forms by the investigator or research coordinator. A summary report of all serious adverse events will be provided to the reviewing IRB annually. Serious adverse events will be reported within 5 days of the investigator learning of the event to the reviewing IRB.

Secondary Endpoints

Burst DBS may require less energy and therefore a secondary endpoint we will include is a calculation of IPG (implanted pulse generator) or battery longevity. Secondary endpoints will also patient preference for stimulation mode.

Statistical Methods

Statistics will be performed using Mann-Whitney-U test and p-value < 0.05 will be required for statistical significance.

Regulatory and Ethical Considerations

Compliance Statement

This study will be conducted in full accordance all applicable Allegheny Health Network Research Policies and Procedures and all applicable Federal and state laws and regulations including 45 CFR 46, 21 CFR Parts 50, 54, 56, 312, 314 and 812 and the Good Clinical Practice: Consolidated Guideline approved by the International Conference on Harmonisation (ICH). All episodes of noncompliance will be documented.

The investigators will perform the study in accordance with this protocol, will obtain consent and assent, and will report unanticipated problems involving risks to subjects or others in accordance with the AHN IRB Policies IRB Policies and Procedures and all federal requirements. Collection, recording, and reporting of data will be accurate and will ensure the privacy, health, and welfare of research subjects during and after the study.

Risk Assessment

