Appendix A

Visit 1 Case Report Form

Date / /
 dd mmm yyyy

Last dose of Parkinson's medications: _____ am / pm

Time DBS device turned off: _____ am / pm

To be completed by unblinded examiner

Subject randomization for initial DBS setting (Circle): Burst / Baseline

Left Right

Active Contacts

Amplitude

Pulse Width

Frequency _____

Subject Programming Preference (Circle): Burst / Baseline / No preference

Comments:

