Appendix A

Visit 2 and 3 Case Report Form

Subject # _____

Date / /
 dd mmm yyyy

Last dose of Parkinson's medications: _____ am / pm

Time DBS device turned off: _____ am / pm

Left Right

Active Contacts

Amplitude

—
—

Pulse Width

Frequency

Frequency _____

Frequency _____

Comments:

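### Patient preference, a secondary endpoint, has three possible answers at Visit 1, but months 6 and 12 ask only about preferring burst, so indifference and preference for the old setting may not be separable

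*Combined protocol and SAP*

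**What the plan says.** The Secondary Endpoints section states: "Secondary endpoints will also patient preference for stimulation mode". It gives no time point, answer scale or rule for counting patients without a preference. The Statistical Methods section names one test for the whole study and nothing specific to preference.

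Preference is asked about at several contacts, in different terms:

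- **Visit 1.** Patients, blinded to the setting, "will be asked if they preferred one stimulation mode over the other". The Visit 1 form in Appendix A has the line "Subject Programming Preference (Circle): Burst / Baseline / No preference".
- **Visits 2 and 3.** "Patients will be asked if they prefer the burst mode DBS state to their baseline settings before the study". No answer options are stated.
- **Phone calls.** "Phone follow up calls will be completed by study personnel to determine subject’s programming preference at 1 week, 1, 3 and 9 months". No question wording or answer options are stated.
- **End of study.** After the Visit 3 question, "patients will be asked if they want to continue to use burst DBS state or if would prefer to be programmed back" to the earlier settings.

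Appendix A also contains a "Visit 2 and 3 Case Report Form". No preference line can be seen on it, but the text of that page is visibly damaged, so nothing here rests on its absence.

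**The concern.** The Visit 1 item is neutral and two-directional, and it treats indifference as an answer in its own right. The question at months 6 and 12 names one direction only. A patient who answers 'no' may prefer the old setting or may not mind either way. If the reply is recorded as it was asked, that distinction cannot be recovered afterwards. The wording also suggests burst as the expected answer.

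The long-term visits are where a lasting preference would show. With 5 completers each patient is 1/5 = 20 percentage points, so the treatment of one or two indifferent patients can decide how the result reads.

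**Working it through.** The plan gives no expected preference share and no calculation for this endpoint, so there is no figure to reproduce. The check asks how often the same five opinions would point in different directions on the two scales.

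**Inputs.** Five completers (Subject Replacement). Three answers (Appendix A, Visit 1 form). The probabilities of each answer are assumptions, varied below. Patients are taken as independent with common shares. The reply at months 6 and 12 is taken as yes/no, which is the natural reading but is not stated.

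**Step 1: possible splits.** Let *b*, *c* and *n* be the numbers preferring burst, preferring baseline and having no preference, with *b* + *c* + *n* = 5. There are 7 × 6 / 2 = 21 splits.

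**Step 2: burst ahead on three answers.** This needs *b* > *c*. Nine splits qualify: (1,0,4), (2,0,3), (2,1,2), (3,0,2), (3,1,1), (3,2,0), (4,0,1), (4,1,0), (5,0,0).

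**Step 3: the same splits recorded as yes/no.** 'Yes' is *b* and 'no' is *c* + *n* = 5 − *b*. 'No' is the majority when *b* ≤ 2. That holds for three of the nine: (1,0,4), (2,0,3) and (2,1,2). Each has at least two patients with no preference. For (2,1,2), the Visit 1 scale shows burst ahead 2 to 1, while a yes/no record shows 2 yes and 3 no.

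**Step 4: probability of one of these three splits.** With shares *p_b*, *p_c* and *p_n*:

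P = 5·*p_b*·*p_n*⁴ + 10·*p_b*²·*p_n*³ + 30·*p_b*²·*p_c*·*p_n*²

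Equal shares give (5 + 10 + 30)/3⁵ = 45/243 = 18.5%. Shares of 0.4/0.2/0.4 give 0.0512 + 0.1024 + 0.1536 = 30.7%.

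| Assumed shares (burst/baseline/none) | Probability |
|---|---|
| 0.45/0.45/0.10 | 3.0% |
| 0.4/0.4/0.2 | 9.3% |
| 0.5/0.3/0.2 | 11.4% |
| 0.6/0.2/0.2 | 12.0% |
| 1/3 each | 18.5% |
| 0.2/0.2/0.6 | 30.2% |
| 0.4/0.2/0.4 | 30.7% |

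**Step 5: direction.** If baseline leads (*b* < *c*), then *b* < *c* + *n* as well, so the reverse change cannot occur. Merging the two kinds of 'no' can only make burst look worse. The leading wording may pull the other way, by an amount the documents give no means to estimate.

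**Step 6: what can still be compared.** Visit 1 can be reduced to burst versus not burst. The (2,1,2) split becomes 2 versus 3, which matches the yes/no record. What is lost at months 6 and 12 is the split within the 3.

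**Step 7: significance.** Even if all five preferred burst, a two-sided sign test gives 2 × 0.5⁵ = 0.0625. The counts themselves are the result, so the categories matter.

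**The case against.** The strongest objection is that no part of the plan states a yes/no scale. The Visit 1 text is also an indirect 'if' question, yet its form has three answers, so the prose alone does not fix the scale. Staff at months 6 and 12 could record three answers, and the neutral wording for the phone calls is close to the label on the Visit 1 form. This stands. A reader might infer that the plan fixes a two-level scale at the later visits, and the documents do not support that. They show a one-directional question with undefined answers.

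It is also fair to say that burst versus baseline and burst versus not burst are different quantities, both true of the same patients, and that 'did not prefer burst' is not 'against burst'. That stands too. The harm arises when the two counts are read as one endpoint over time, and the plan gives no rule to prevent it.

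The end-of-study question might be taken as a third preference scale. The plan does not call it the endpoint; it reads as a decision about continuing care, so no weight is placed on it here.

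Finally, a common scale would not make the contacts fully comparable. Visit 1 answers are blinded and follow 30 minutes on each mode the same day. Later, only burst is applied, the question names it, no blinding to mode is described, and the old setting must be recalled. This is correct and limits what the fix can achieve. It is no reason to keep an avoidable second difference.

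**Conclusion.** The point holds as an inconsistency in how a named secondary endpoint is elicited. It goes beyond missing detail, because the wording at the two long-term visits names one direction and a plain 'no' to it cannot be resolved later.

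A reader might infer that Visit 1 answers cannot be compared with later ones at all. That is too strong, since comparison as burst versus not burst remains possible. A reader might also infer that a reversed direction is to be expected. The arithmetic shows only that it can happen: 3 of the 9 splits where burst leads, each needing at least two patients with no preference. The range of about 3% to 31% rests on assumed shares, independent patients and a yes/no record.

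The primary objective is unaffected, and no significance claim on preference is within reach at this sample size. The change is worth making because it costs almost nothing and must be in place before the answers are collected.

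**What to change.** Replace the question in the Visit Two and Visit Three text with the Visit 1 item in neutral form, for example: *Which setting do you prefer: burst, your pre-study setting, or no preference?* Put the same line on the Visit 2 and 3 form and in the script for all four calls (1 week; 1, 3 and 9 months). At Visit 1, where the patient is blinded, ask about the first or second setting and have the unblinded examiner transcribe the answer.

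In Secondary Endpoints, name the main time point and state that counts in all three categories will be reported at each contact, with no preference kept as its own category. Report the end-of-study choice to continue burst or return to the pre-study settings separately. For the (2,1,2) split, that two-way choice could come out anywhere from 2:3 to 4:1, depending on the two undecided patients.

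State that any change from Visit 1 is descriptive, because Visit 1 is blinded with same-day exposure to both modes and later answers are unblinded and rely on recall.

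The cost is a few lines in the visit text, one line on the form and one in the phone script. No visit, patient, staff or change in clinical management is added.

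### Read literally, the Mann-Whitney p < 0.05 rule covers patient preference, but it does not fit one choice per patient; report counts with an exact interval over all randomised patients

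*Combined protocol and SAP*

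**What the plan says.** The Secondary Endpoints section lists battery longevity and then preference: "Secondary endpoints will also patient preference for stimulation mode". A verb has dropped out, but the meaning is clear. The Statistical Methods section that follows is one sentence: "Statistics will be performed using Mann-Whitney-U test and p-value < 0.05 will be required for statistical significance". It names no endpoint, sidedness or exception, and the protocol contains no other analysis text.

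The form of the data comes from the visit descriptions and Appendix A:

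- **Visit 1.** Each patient receives both modes in randomised order, blinded to setting, and is then asked which was preferred. The case report form records "Subject Programming Preference (Circle): Burst / Baseline / No preference".
- **Visits 2 and 3.** Each patient is asked whether burst is preferred to the pre-study settings. At Visit 3 there is also a choice of mode to continue with.
- **Phone calls.** Preference is asked at one week and at one, three and nine months.

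That makes seven scheduled occasions, and none is named as the main one.

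On numbers, the Study Design section gives "Randomized, double-blind cross-over study with N= 5 patients implanted with bilateral subthalamic nucleus DBS". Subject Replacement lets the investigator "screen and enroll replacement subjects(s) to ensure the number of completed subjects equals 5", and an adverse reaction to burst programming is one of its listed reasons for withdrawal. Recruitment Strategy adds "It is expected that approximately 15 subjects will be enrolled to produce 5 evaluable subjects", although its preceding sentence stops recruitment at about 5 enrolled.

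**The concern.** A test for two independent groups is the only method in the plan, and a single choice made within each patient is one of its endpoints. An analyst who follows the text literally must either recode the answers until they resemble two groups, which counts each patient twice, or depart from the plan and choose a method after seeing the data. At this sample size the choice of method, its sidedness and the patients counted can each change the reported result on identical answers.

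The second issue is who is counted. If the tally is limited to the 5 who complete, patients who left because burst did not suit them drop out of it and others take their places. With so few patients, and publication planned, preference is one of the results that readers will find easiest to interpret, so its denominator should be fixed in advance.

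**Working it through.** The plan states no null value, power or sample-size calculation for preference, so there is no figure of its own to reproduce.

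**Inputs.** From the documents: 5 patients, significance at p < 0.05, one three-category answer per patient per occasion. Assumptions: a null preference rate of 0.5, with both one-sided and two-sided results shown because the plan states neither.

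**Step 1: can Mann-Whitney be applied?** There are two ways to force it.

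- *Enter each answer twice*, as 1 for the chosen mode and 0 for the other. Unanimity gives five 1s against five 0s, and the exact two-sided p is 2 / C(10,5) = 2/252 = 0.0079. This is spurious: ten values come from five patients, and within each patient one value determines the other.
- *Compare the two randomised order groups.* The most even split of 5 is 2 against 3. The smallest exact p is 1 / C(5,2) = 0.10 one-sided, or 0.20 doubled. These groups are independent, but the comparison asks whether order affected preference, not which mode is preferred.

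**Step 2: an exact binomial test against 0.5, if one were used.**

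| Preferring burst / stating a preference | One-sided p | Two-sided p |
|---|---|---|
| 5/5 | 0.5^5 = 0.03125 | 2 × 0.03125 = 0.0625 |
| 4/5 | (5 + 1)/32 = 0.1875 | 0.375 |
| 4/4 (one of 5 has no preference and is excluded) | 0.5^4 = 0.0625 | 0.125 |
| 6/6 | 0.5^6 = 0.0156 | 0.03125 |

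With 15 answers, 12/15 is enough: (455 + 105 + 15 + 1)/32768 = 0.0176 one-sided, 0.035 two-sided.

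**Step 3: exact (Clopper-Pearson) 95% intervals.**

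- 5/5: the lower limit solves p^5 = 0.025, so p = 0.025^(1/5) = 0.478. The interval is 48% to 100%.
- 4/5: the upper limit solves 1 − p^5 = 0.025, so p = 0.995. The lower limit solves 5p^4(1 − p) + p^5 = 0.025, so p = 0.284. The interval is 28% to 99%.

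**Step 4: effect of the denominator.** As an illustration only, suppose all 5 completers prefer burst and r replaced patients did not. A completers' tally shows 5/5 = 100%. Over all randomised patients the share is 5/(5 + r):

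- r = 1: 5/6 = 83%
- r = 2: 5/7 = 71%
- r = 10: 5/15 = 33%

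The last is an outer limit. It takes the expected 15 enrolled as all randomised, and enrolment may include people who never reach randomisation.

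**The case against.** The best counter-argument is that the plan never says preference will be tested. The Mann-Whitney sentence names no endpoint, and the other secondary endpoint is described simply as a calculation, so not every endpoint need be meant for a test. On that reading preference would just be described, and no harm follows. This stands in part: the rule's reach to preference is inferred from its unrestricted wording. But the alternative is that preference has no analysis specified at all, and the same sentence of text is needed to correct that.

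Two stronger readings are tempting, and the documents support neither.

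- *That 5 patients can never give a significant preference.* This holds only for a two-sided test with exactly 5 answers. The plan states no sidedness, and one-sided 5/5 gives 0.031. The number of patients giving an answer may also exceed 5, and 6/6 is significant two-sided. The binomial test itself is a substitute introduced here, not something the plan proposes.
- *That a unanimous preference would be reported as negative.* Nothing in the text prevents counts from simply being described.

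It is also fair to say that preference is a secondary endpoint in a very small study. That limits the weight of the point, but the correction is almost free.

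**Conclusion.** The concern holds in limited form. The one named test does not fit a single within-patient choice, and this does not depend on the sample size or sidedness. Applied literally to unanimous answers, it could yield p = 0.008 by counting each patient twice.

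The 0.0625 floor is conditional on an exact binomial test, a null of 0.5, two sides and 5 answers. It should be cited only with those conditions.

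The denominator problem rests on the replacement rule. Because a bad reaction to burst is a listed ground for withdrawal and replacement, a completers-only tally would tend to favour burst. The documents do not say how many such patients to expect, so the direction is clear but the size is not.

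Even a unanimous result in 5 patients is compatible with a true share preferring burst as low as 48%, so an interval tells the reader more than a significance label.

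**What to change.** In Statistical Methods, exclude preference from the Mann-Whitney p < 0.05 rule and add text along these lines:

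> Preference will be summarised without a significance test. The main time point is the blinded answer at Visit 1. Numbers answering burst, baseline and no preference, and the number with no answer, will be given for all randomised patients, including those later withdrawn and replaced. The share preferring burst will be given over all randomised patients with an exact 95% confidence interval. Answers at later visits and by phone will be described separately at each time point, with missing answers shown as their own count.

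Visit 1 is the right anchor because it is the only occasion on which a blinded patient compares both modes in one session. At Visits 2 and 3 the question itself names burst, and there is no blinded comparison. With this denominator, no preference and missing answers count as not preferring burst. The text should say so, since a share among only those stating a preference is a different quantity.

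The cost is a few lines of text, with no new visits or questions. The downside is that there will be no p-value for preference.
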